10.5. Statistical Analysis

Between group differences in the change in mean adherence from baseline over will be based on a 0.05 level t-test. The corresponding 95% confidence interval for the between group mean difference will provide an interval estimate of benefit obtained using the Cohero system. [NR1]

In addition to the frequentist analysis of adherence, a Bayesian approach that focuses on estimating the probability distribution of differences in mean adherence using the Cohero system compared to standard of care. The Bayesian approach begins with the premise that the Cohero system yields no improvement in adherence. This is an exact correspondence to a “null hypothesis”. This assumption is incorporated through a prior distribution for improvement in mean adherence; for example, by assuming that the mean improvement is characterized by a normal distribution with mean 0, the expected difference should the Cohero system offer no benefit, and some small variance (e.g. 0.01). This is also a statement that the probability that the Cohero system improves response compared to standard of care is 50% (i.e., the prior odds that active therapy is effective is 1:1, consistent with the notion of equipoise).

The essence of the Bayesian approach is to use the data collected during the study to update the prior probability density based on the observed data (this updated density is the posterior probability distribution) using Bayes Theorem. This posterior distribution provides estimates of the probability that the Cohero system improves adherence relative to standard of care by any amount greater than δ . For example, choosing $\delta=0$ corresponds to the frequentist test of the null hypothesis.

The analysis of lung function will be performed in a corresponding manner to that described for adherence. Additionally, the correlation between change in FEV1, FEV1/FVC ratio and FEF25-75 and change in adherence will be computed. Graphical analysis will be used to visually inspect the relationship between improvement in adherence and improvement in lung function. Based on the general form of the relationship, additional exploratory analyses will be performed. For example, if the relationship is approximately linear, standard regression methods will be used to estimate the relationship; if, however, a clear discontinuity is seen, splines might be used to estimate the relationship.

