7. STUDY POPULATION

This study will enroll children who have been diagnosed with persistent asthma for at least 6 months' duration and who are showing evidence of poorly controlled disease. 75 children will be recruited from CT Children's Medical Center Pulmonary Clinic and East and West Primary Care.

7.1.Inclusion and Exclusion Criteria

Inclusion and Exclusion Criteria

Inclusion criteria:

- Age 8 to 17
- Diagnosis of persistent asthma
- Prescribed an inhaled corticosteroid (ICS) for at least one month prior to enrollment
- Use of a pressurized metered dose inhaler (pMDI) compatible with the Cohero mHealth Herotracker (See Appendix)
- Parent/child possess a compatible smartphone (iOS 8.0 or higher)
- English or Spanish speaking

Exclusion criteria:

- Presence of another chronic lung disease or condition such as cystic fibrosis, interstitial lung disease, chronic lung disease of prematurity, recurrent aspiration, or presence of tracheostomy
- Presence of other chronic medical condition such as congenital heart disease or immunodeficiency
- Presence of other comorbidities that, in the opinion of the investigator, will interfere with collection of study procedures, or limits life expectancy to < 1 year
- Currently pregnant or planning to become pregnant during the trial period

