8.2. Randomization

If the child is eligible and they wish to participate they will be randomized in a 2:1 allocation to BreatheSmart or to standard of care. As we have a limited supply of HeroTracker devices and the CoHero platform does not provide a feasible way to execute any degree of blinding, this will be conducted as an open trial where both groups (control and intervention groups) will be treated as equally as possible. Randomization will be stratified by age at the time of enrollment (8-13 years, 14-17 years) and blocked in randomly permuted sequences of 4.

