8.3. Baseline Assessments

8.3.1. Control Participants

Control participants will be reminded to adhere to the standard of care therapy, as prescribed. The following assessments will be recorded:

- Concomitant medications

- Measurement of lung function including FEV1, FEV1/FVC ratio, FeNO (standard clinic measurement only assessed in the Pulmonary clinics)
- Child Asthma control test (ACT) questionnaire
- Exacerbation of asthma episodes (obtained through self-report and chart review) requiring:
 - Courses of oral steroids
 - Doctor visits outside of standard of care
 - ER visits
 - Hospitalizations
- Missed school days
- PedsQL asthma module (patient and parent report)
- Test of Adherence to Inhalers
- Pharmacy refill data for asthma prescriptions during the previous 6 months

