8.4. Follow-up

All participants in both groups will be seen at 90 and 180 days' post randomization (+/-20 days) correlating with routine pulmonary clinic follow up and East and West Primary Care Follow up where the following assessments will be recorded:

- Medication changes/refills (obtained through pharmacy record)

- FEV1, FEV1/FVC, FEF25-75 and FeNO per clinical standard of care (only assessed in the Pulmonary clinic)
- Child Asthma control test (ACT) questionnaire
- Serious Adverse Events will be recorded at each visit
- Missed school days
- PedsQL asthma module (patient and parent report)
- Test of Adherence to Inhalers
- Exacerbation of asthma episodes (obtained through self-report and chart review) requiring:
 - Doctor visits outside of standard of care
 - ER visits
 - Hospitalizations

In addition, active participants (test group) will be continuously monitored via the CoheroConnect dashboard which allows the Investigator to monitor the child's medication adherence in real time. If a period of participant inactivity of 3 days is registered in the system, the Investigator (or designee) will be notified and he/she will be prompted to contact the participant to remind them to take their medication as prescribed. The Investigator or designee will review patient specific data (% adherence since last visit and graph of adherence patterns over time since enrollment) through the CoheroConnect dashboard within two days before a follow up visit. At the follow-up visit, these data will be reviewed with the patient and parent/caregiver. The adherence rate and barriers identified will be discussed and, if necessary, personalized strategies for improvement will be devised. These data will also be shared with the clinician during these follow up visits. Medication adherence data for control participants will be obtained by measure of pharmacy record refill information and self-report (Test of Adherence to Inhalers) throughout the duration of the study.

We understand that the self-report of missed school days due to asthma may be unreliable and subject to recall bias, however, this is the method we currently use clinically to assess this measure.

If a participant is unable to complete the follow-up visit at their routine pulmonary appointment, the coordinator will either mail, text a link, or email a link of the follow-up surveys to the participants. They will be reminded 3 times via text, email or phone to complete the follow-up questionnaires.

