10.4. Data analysis

All data will be analyzed in accordance with the statistical analysis plan (SAP) to be developed at the beginning of this study. Both primary and secondary analyses will be based on an intention-to-treat (ITT).

The study's primary objective is to estimate the relative improvement in medication adherence among children using the BreatheSmart compared to control participants using "standard of care".

Important secondary objectives include the extent to which the Cohero system improves:

- asthma control as measured by ACT

- FEV1, FEV1/FVC ratio, FEF25-75 and FeNO compared to standard of care, and the correlation between changes in medication adherence from baseline and changes in FEV1 and FEV1/FVC ratio.
- the overall number of provider visits for asthma-related adverse outcomes (number of exacerbations leading to Provider intervention, ER visits, hospitalizations, or requiring oral systemic corticosteroid therapy)
 - Missed school days

Data results may be used to inform a study of a larger cohort with similar focus with regard to sample size estimates, efficacy of the BreatheSmart platform, feasibility in a low-income pediatric population and study design.

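### The primary t-test on change from baseline fixes the baseline coefficient at 1 and leaves out the age stratum used to randomise; a baseline-adjusted model would usually give a narrower interval

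*Combined protocol and SAP*

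**What the plan says.** Section 10.5 of the combined protocol and SAP sets the primary comparison: "Between group differences in the change in mean adherence from baseline over will be based on a 0.05 level t-test". The sentence names no time point; section 6.1.1 supplies 6 months. It continues: "The corresponding 95% confidence interval for the between group mean difference will provide an interval estimate of benefit obtained using the Cohero system". It does not say whether the t-test is pooled or Welch, and it names no covariate. Lung function is to be handled in the same way.

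Section 8.2 states: "Randomization will be stratified by age at the time of enrollment (8-13 years, 14-17 years"). Neither section 10.4 nor section 10.5 uses that factor. Regression is mentioned only for the exploratory link between adherence and lung function.

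Section 10.4 states: "All data will be analyzed in accordance with the statistical analysis plan (SAP) to be developed at the beginning of this study". Nothing in the supplied text adds an adjustment.

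A baseline value is planned. Sections 8.3.1 and 8.3.2 list, for both arms, "Pharmacy refill data for asthma prescriptions during the previous 6 months", together with a self-report adherence test.

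**The concern.** Subtracting baseline amounts to assuming that a child who starts 10 points higher will, without treatment, finish 10 points higher. Refill or self-report adherence is a noisy measure and is likely to regress towards the mean. The entry rule, "Prescribed an inhaled corticosteroid (ICS) for at least one month prior to enrollment", also means that some children may have a short refill history. A coefficient of 1 would then be too large, and subtraction would add noise.

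The confidence interval is the plan's stated estimate of benefit, and sections 7.2 and 10.4 intend the results to inform the size of a larger study. The sample is capped by the supply of 50 devices, with 25 controls, so the choice of analysis is one of the few ways left to improve precision.

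**Working it through.** **Inputs from the documents.** 50 and 25 children (section 6); two-sided 0.05, implied by the 95% interval; two age strata (section 8.2). The plan states no power, SD, effect or interval width, so it has no figure to reproduce.

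**Assumed inputs.** Baseline to 6-month correlation ρ of 0.3 to 0.9; SD of 25 points at both times, with 20/25 and 25/20 (baseline/6-month) as variants; effect of 15 points; normal data; no dropout.

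**Step 1: what the t-test assumes.** Comparing Y₁ − Y₀ between arms is the model Y₁ = a + b·arm + 1·Y₀ + error. The least-squares slope is ρ·s₁/s₀, which equals 1 only in special cases.

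**Step 2: variance ratio, adjusted model to change score.**

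Ratio = s₁²(1 − ρ²) / (s₀² + s₁² − 2ρs₀s₁), which is (1 + ρ)/2 when s₀ = s₁.

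Example, 20/25 at ρ = 0.5: 625 × 0.75 / (400 + 625 − 500) = 468.75/525 = 0.89.

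| SDs (baseline/6-month) | ρ 0.3 | ρ 0.5 | ρ 0.7 | ρ 0.9 |
|---|---|---|---|---|
| equal | 0.65 | 0.75 | 0.85 | 0.95 |
| 20/25 | 0.78 | 0.89 | 0.98 | 0.95 |
| 25/20 | 0.50 | 0.57 | 0.63 | 0.61 |

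With equal SDs the change score has variance 2(1 − ρ) in units of SD². Below ρ = 0.5 this exceeds 1, so the change-score interval is wider than one that ignores baseline altogether.

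**Step 3: half-width by formula, ordinary standard errors, ρ = 0.5, SD 25.**

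- Change score: t(0.975, 73) × 25 × √[2(1 − 0.5)(1/50 + 1/25)] = 12.2 points.
- Adjusted for baseline and age: t(0.975, 71) × 25 × √[(1 − 0.25)(1/50 + 1/25)(1 + 2/70)] = 10.7 points. The last factor allows for chance covariate imbalance.

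The ratio of half-widths is 0.82, 0.88, 0.94 and 0.99 at ρ 0.3, 0.5, 0.7 and 0.9. With 40 and 20 completers it is almost the same.

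**Step 4: simulation of the proposed model.** Welch t-test on change against regression on arm, baseline and age with HC3 standard errors, SD 25.

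| ρ | Welch half-width | HC3 half-width | Welch power, 15 points | HC3 power, 15 points |
|---|---|---|---|---|
| 0.3 | 14.5 | 12.1 | 52% | 68% |
| 0.5 | 12.2 | 11.0 | 67% | 77% |
| 0.7 | 9.5 | 9.1 | 88% | 92% |
| 0.9 | 5.5 | 5.5 | >99% | >99% |

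Repeat runs agree to about 0.1 point of half-width and 2 points of power. Type I error was 4.8% to 5.2% for Welch and 4.4% to 5.0% for HC3. The adjusted interval was narrower in 98%, 92%, 74% and 37% of trials at ρ 0.3, 0.5, 0.7 and 0.9.

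At ρ = 0.5, (12.2/11.0)² = 1.23, so the gain is worth about 23% more children.

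**Step 5: the age term alone.** If age shifts only 6-month adherence by 10 points, adding it to a baseline-only model raises power from 66.9% to 69.4% (ρ 0.3), 75.0% to 77.1% (0.5) and 88.9% to 90.8% (0.7). If age shifts both times equally, the gain is under 1 point.

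**The case against.** The strongest reply is that nothing in the plan is wrong. A change-score t-test in a randomised trial is unbiased, the study is declared exploratory, and there is no power target to miss. That is correct, and it limits this to a recommendation about precision.

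The variance ratios in step 2 also flatter the proposed model, because they ignore the cost of HC3, about 3% of interval width compared with ordinary standard errors. With SDs of 20/25 the HC3 interval is slightly wider than Welch: 9.08 against 8.83 at ρ 0.7, and 5.52 against 5.46 at ρ 0.9. This stands. In those cells the fitted slope is 0.7 × 25/20 = 0.875 and 0.9 × 25/20 = 1.125, so a fixed value of 1 is nearly right. The loss there is at most 3%.

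The power contrast depends on the effect chosen. Section 1 cites improvements of 10 to 52 points. At 25 points power is 92.5% against 98.3% (ρ 0.3) and 97.5% against 99.2% (ρ 0.5); at 30 points both exceed 98%. Interval width does not depend on the effect, and it is what the plan reports as its estimate.

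The SAP still to be written could add covariates. It could, but the only test named so far is the unadjusted one.

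A larger question comes first. Section 8.4 states: "Medication adherence data for control participants will be obtained by measure of pharmacy record refill information and self-report". The intervention arm also has sensor data, neither arm has a sensor baseline, and the plan does not say which measure is primary. Adjustment cannot repair a difference in measurement between arms. This stands as a precondition for the fix.

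**Conclusion.** The point holds as a recommended change. The planned test is valid if the arms' variances are similar or Welch is used, but it is usually the less precise choice. With equal SDs of 25 points, adjustment with HC3 errors narrows the interval by about 17% at ρ 0.3 (12.1/14.5 = 0.83), 10% at 0.5 (11.0/12.2 = 0.90) and 4% at 0.7 (9.1/9.5 = 0.96), with nothing gained at 0.9. The gain is larger if adherence varies less at 6 months than at baseline, and small or slightly negative if it varies more and ρ is high. Every SD and correlation here is assumed. Age contributes little; it belongs in the model because it was a randomisation stratum. Confidence in the size is moderate, because ρ is unknown.

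**What to change.** First settle one adherence measure that both arms have at baseline and at 6 months. Then replace the t-test sentence in section 10.5 with:

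> Adherence at 6 months will be compared between arms by linear regression on arm, baseline adherence (same measure as at follow-up, in both arms) and age stratum (8-13, 14-17), with HC3 standard errors. The arm coefficient and its 95% confidence interval are the primary estimate.

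In addition:

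- Keep a t-test on change as a sensitivity analysis, and name it as Welch.
- State how baseline adherence is computed for children with under 6 months of ICS refills.
- Say whether the Bayesian analysis in section 10.5 uses the same adjusted model, so that the two analyses estimate the same quantity.
- Use the same model for FEV1 and FEV1/FVC, each with its own baseline. Section 8.4 limits these measurements to the pulmonary clinic, so the figures for 75 children do not apply to them.

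The cost is SAP wording and two residual degrees of freedom (75 − 2 = 73 becomes 75 − 4 = 71). No new data are needed if the common measure is refill or self-report adherence.

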Telemanagement of chronic diseases is increasingly being employed to improve medication adherence and health outcomes, and has been shown to be cost-effective.¹³ A recently developed process model for optimal asthma care demonstrates the need for improved understanding of patient medication use behavior and how adherence interventions can impact clinical outcomes.¹⁴ A number of studies have improved medication adherence through incorporation of electronic reminders such as text messages across the spectrum of chronic diseases.¹⁵ Recently a number of studies have looked specifically at the use of such messages along with medication-use tracking in asthma have been able to show mean improvement in adherence from 10-52 percentage points.¹⁶⁻²³ While promising, these interventions have focused on the use of audiovisual reminder systems^{16, 21-23} that rely on having access to the inhaler itself or are simply based on SMS messages.^{17,18} Such interventions are limited in their ability to engage participants for improved disease self-management and self-monitoring compared to more comprehensive approaches, known to be key for sustained asthma telemanagement and mHealth approaches.¹³

Importantly, mobile applications allow for better sustained patient engagement and have been successfully implemented in other disease spaces to improve medication adherence and outcomes.¹³ Mobile applications offer the opportunity to be scaled to the U.S. population-at-large and can be sustained due to the front-end cost of development and low staff resources required for maintenance once the product is built. Additionally, the ability to relay adherence data directly to clinicians either via a patient portal or into the EMR provides opportunity to direct care coordination efforts and resources towards those participants who are most in need, and provides information that can be used for point-of-care treatment decision making.

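### Does the loosely specified Bayesian prior for adherence in section 10.5 need to be tightened?

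*Combined protocol and SAP*

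**What the plan says.** Section 10.5 compares the arms on change in mean adherence with a t-test at the 0.05 level and a 95% confidence interval. A Bayesian analysis is added to this. Its prior for the improvement in mean adherence is introduced as an example: normal, with "mean 0, the expected difference should the Cohero system offer no benefit, and some small variance (e.g. 0.01" as the variance. The section equates this with a 50% prior probability of benefit, that is, equipoise. The posterior is then to give the probability that the system "improves adherence relative to standard of care by any amount greater than" a threshold delta. Zero is the one value named, again as an example, and the section says that it "corresponds to the frequentist test of the null hypothesis".

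On lung function, section 10.5 says: "The analysis of lung function will be performed in a corresponding manner to that described for adherence". Section 8.4 notes that these measurements are "only assessed in the Pulmonary clinic".

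Two other places bear on the point. Section 7.2 says that there are no pilot data and calls the study exploratory. Section 10.4 refers all analyses to a "statistical analysis plan (SAP) to be developed at the beginning of this study".

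**The concern.** A posterior probability is only as well defined as its prior. Here the variance is an example, it has no unit, and no second prior is planned to show how much it matters. The stated 50% does not pin it down, because every normal prior centred on zero gives 50%.

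The unit is a fair question. Elsewhere the document speaks of adherence in percent: section 8.4 has the dashboard show % "adherence since last visit and graph of adherence patterns over time since enrollment", and section 1 says that earlier studies could "show mean improvement in adherence from 10-52 percentage points". On a 0-1 scale the example prior puts 95% of its mass within 19.6 points of zero, so much of what section 1 reports lies beyond it. On a percent scale the same number would all but fix the answer at no effect. Lung function has no prior of its own, and 0.01 would mean something different for FEV1 and for FEV1/FVC.

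The trial is open (section 8.2). An analyst who picked the variance or the threshold after seeing the data could move the reported probability of a worthwhile gain from unlikely to likely, and section 10.4 says the results may inform a larger study.

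**Working it through.** **Inputs.** From the document: 50 and 25 children (section 6); prior mean 0 and example variance 0.01 (section 10.5); a literature range of 10 to 52 points (section 1). No SD is given, so the SD of change in adherence is assumed: 0.30 on the 0-1 scale for the main case, with other values below. The 20-point observed gain is also assumed. Full follow-up and a normal approximation are used.

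**The plan's own figure.** For a N(0, v) prior, P(> 0) = 0.500 at v = 0.01, and equally at 0.0025 and 0.04. The stated 50% is reproduced but does not identify v.

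**Which scale?** On 0-1, v = 0.01 gives an SD of 0.10, a 95% range of ±1.96 × 0.10 = ±0.196, and a prior P(> 0.10) of 0.159. That is sceptical but usable. In percent, the SD would be 0.1 of a percentage point and the 95% range about ±0.2 points. With SDs of 15 to 40 points, even a 52-point observed gain would then leave P(> 0) at only 0.65 to 0.52. No data from this trial could move such a prior, so it cannot be the one meant.

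**Update on the 0-1 scale.** SE = 0.30 × √(1/50 + 1/25) = 0.0735, so SE² = 0.0054. The weight on the data is w = v/(v + SE²), the posterior mean is w × 0.20, and the posterior SD is √w × SE.

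| Prior variance | w | Posterior mean (points) | P(> 0) | P(> 10 points) |
|---|---|---|---|---|
| 0.0025 | 0.316 | 6.3 | 0.937 | 0.187 |
| 0.01 | 0.649 | 13.0 | 0.986 | 0.693 |
| 0.04 | 0.881 | 17.6 | 0.995 | 0.865 |
| Data alone | 1 | 20.0 | 0.997 | 0.913 |

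The plan's example at a threshold of zero differs from the data-alone answer by 0.997 − 0.986 = 0.011. The wide spread is in the last column, whose threshold is an illustration taken from the low end of section 1's range.

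**Less favourable data.** With a 15-point observed gain, P(> 0) for variances 0.0025, 0.01 and 0.04, then data alone, is:
- SD 0.20: 0.986, 0.997, 0.999; 0.999
- SD 0.30: 0.875, 0.950, 0.972; 0.979
- SD 0.35: 0.811, 0.908, 0.946; 0.960

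So sensitivity at zero grows when the data are weak, but at the example variance the result stays within 0.960 − 0.908 = 0.052 of the data-alone figure in these cases.

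**The link with the t-test.** With a flat prior, P(> 0) equals one minus the one-sided p-value. In the main case the two-sided p is 0.0065, so this is 1 − 0.0065/2 = 0.997, as in the table. Under the example prior it is 0.986. The correspondence is therefore in the null value and not in the number.

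**The case for a change.** The strongest case for acting is that the omissions are real and cheap to repair. Nothing in the document fixes the variance, the unit or a prior for lung function. Three variances that could each be called small give 0.19, 0.69 and 0.87 for a gain above 10 points, and a few sentences written before outcome data are examined would remove that freedom. This stands as a description of missing detail.

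It does not show that a planned result would be wrong. The large spread belongs to a threshold the plan does not name. Section 10.5 promises a posterior distribution, from which the probability for any threshold can be read. The printed 0.01 is also a public reference point, so a departure from it would be visible.

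The supporting arguments are weaker:
- A sceptical prior is expected to sit closer to zero than the published gains, and section 10.5 gives its reason: start from no improvement, at equipoise. Section 1 gives only the ends of a range, so the share of it lying beyond the prior's 95% limits has no probability meaning.
- One can construct cases where a 95% credible interval covers zero and the confidence interval does not. At SD 0.35 and a 20-point gain they are −1.2 to 24.3 and 3.2 to 36.8. But section 10.5 plans only the confidence interval and sets no rule on a Bayesian interval.
- The variance of 0.01 is attached to adherence alone. Nothing says that it carries over to lung function, where any analyst must choose a prior in the unit of the outcome.
- A second, wider prior is a reasonable preference, but its width would be a judgement too.

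**Conclusion.** No change to the plan is called for. This is a gap that analysts fill sensibly. The text presents the prior as an illustration, only the 0-1 scale makes it usable, and on that scale it is an acceptable sceptical prior. Recording the scale, the variance, the thresholds and the lung-function priors is ordinary content for the SAP that section 10.4 announces. That SAP is not among the documents, so its absence here is not evidence that these items were left open.

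At the one threshold named, variances from 0.0025 to 0.04 move the probability of benefit between 0.937 and 0.995 in the main case, and between 0.811 and 0.946 in the least favourable of the 15-point cases shown. A reader should treat any reported probability of a gain above 10 points with more caution, since it runs from 0.19 to 0.87 in the main case. These figures rest on assumed SDs and gains, full follow-up and a normal approximation. The t-test and its confidence interval do not depend on the prior.

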7.2. Sample Size Estimates

There is no pilot data available to inform a sample size analysis. In addition, our sample size is limited by our supply of HeroTracker devices (50). As this is an exploratory study, we hope our findings will inform future sample size analyses for studies of similar focus with a larger cohort.

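### Is it an error for section 10.5 to say that δ = 0 corresponds to the frequentist test, when its small-variance prior is centred on zero?

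*Combined protocol and SAP*

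**What the plan says.** Section 10.5 makes a t-test at the 0.05 level, with a 95% confidence interval, the analysis of the between-group difference in change in adherence. The Bayesian analysis is introduced with "In addition to the frequentist analysis of adherence", so it is an addition and not a replacement. Its prior for the mean improvement is normal with mean 0 and "some small variance (e.g. 0.01" in the text's example. The section says of the no-improvement premise "This is an exact correspondence to a" null hypothesis, and then of the prior: "This is also a statement that the probability that the Cohero system improves response compared to standard of care is 50" per cent, which it links to equipoise. The posterior is to give the probability that the improvement exceeds a chosen δ, and taking δ = 0 "corresponds to the frequentist test of the null hypothesis".

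For spirometry, "The analysis of lung function will be performed in a corresponding manner to that described for adherence". Section 10.4 refers all analyses to a "statistical analysis plan (SAP) to be developed at the beginning of this study". Section 7.2 gives the status of the trial: "As this is an exploratory study", with no pilot data and a sample size limited by the supply of devices.

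**The concern.** The posterior probability of a positive difference equals 1 minus the one-sided p-value only when the prior is close to flat. Section 10.5 asks for the opposite, a prior tight around zero, and attaches no condition to the sentence on δ = 0. A reader could take the posterior probability of benefit as the t-test in Bayesian form. That reader would be puzzled by a result exactly at p = 0.05, where the confidence interval touches zero and the credible interval crosses it. The earlier phrase about exact correspondence to a null hypothesis encourages this reading, because a continuous prior that gives benefit an even chance expresses equipoise or scepticism and is not a point null. If the reading took hold, the probability of benefit could be misquoted when the results are used to plan a larger study, as section 10.4 foresees.

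**Working it through.** **The plan's own figure.** Under a normal prior with mean 0 and variance 0.01, the probability of a positive improvement is 0.50. This matches the 50% in section 10.5, as it would for any variance.

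**Inputs.** Group sizes are 50 and 25 (section 6). The prior mean is 0 and the example variance V is 0.01 (section 10.5). The documents give no SD for change in adherence and no unit for adherence. I assume a proportion from 0 to 1 and an SD of 0.25, with a range of 0.15 to 0.35.

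**Formulas.** With the standard error treated as known:

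- SE = SD × √(1/50 + 1/25) = SD × √0.06
- weight on the data: w = V / (V + SE²)
- P(difference > 0 given data) = Φ(z × √w)
- z needed for a posterior probability of 0.975 = 1.96 / √w

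Because w is below 1 for any finite V, exact agreement with 1 minus the one-sided p-value (0.975 at z = 1.96) needs a flat prior.

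**Results at z = 1.96, V = 0.01.**

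| Assumed SD | SE | w | P(benefit) | z needed for 0.975 | Two-sided p at that z |
|---|---|---|---|---|---|
| 0.15 | 0.0367 | 0.881 | 0.967 | 2.09 | 0.037 |
| 0.25 | 0.0612 | 0.727 | 0.953 | 2.30 | 0.022 |
| 0.35 | 0.0857 | 0.576 | 0.932 | 2.58 | 0.010 |

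With a t likelihood on 73 degrees of freedom and a result at two-sided p = 0.05, the probabilities are 0.967, 0.952 and 0.931. With V = 1 that calculation gives 0.975 at all three SDs.

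**Intervals at SD 0.25.** The observed difference is 1.96 × 0.0612 = 0.120, with 95% confidence interval 0.000 to 0.240. The posterior mean is 0.727 × 0.120 = 0.087 and the posterior SD is √0.727 × 0.0612 = 0.052, so the 95% credible interval is −0.015 to 0.190.

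**Direction.** The pull is toward 0.5. It lowers the probability of benefit when the observed difference favours the system and raises it when it does not. For an observed −0.05 at SD 0.25, the probability is 0.243 with V = 0.01 and 0.208 with V = 1.

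**Unit of adherence.** If adherence were in percentage points with an SD of 15 to 35, and 0.01 were taken literally, SE² would be 13.5 to 73.5, w would be 0.00074 to 0.00014, and P(benefit) at z = 1.96 would be about 0.52 to 0.51. The prior would swamp the data. Its central 95% range would be ±1.96 × 0.1 = ±0.2 percentage points, whereas section 1 cites improvements of 10 to 52 percentage points. On the proportion scale the same prior spans ±0.196, or about ±20 percentage points. The example makes sense only for a proportion.

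**What the sentence claims.** Its subject is the choice of δ, which the sentence before it defines as the threshold for improvement. Setting the threshold to zero asks whether there is any benefit, and zero is the boundary that the t-test examines. The section does not mention a p-value, a one-sided test or equality of the two numbers.

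**The case for a change.** The strongest case for a change is that the sentence is unconditional, follows a phrase about exact correspondence, and sits beside the kind of prior for which numerical agreement fails. Rewording would cost almost nothing while the SAP is still to be written, and section 10.4 says the results may inform a larger study.

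The arithmetic in this case stands for every SD examined. It is also true that the wording is loose and that a continuous prior is not a point null. The rest does not lead to a change. The same paragraph says that the analysis starts from no improvement, that this enters through a prior centred on zero with small variance, and that benefit has even prior odds. A reader is therefore told why the posterior can be more cautious than the confidence interval, although shrinkage is not named. A second, near-flat posterior would nearly reproduce the t-test and so add little beyond it. A larger study can take its effect estimate and interval from the t-test analysis, which the prior does not touch.

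The more substantial gap is that section 10.5 fixes neither the prior variance nor the unit of adherence, and the percentage-point calculation shows that this could matter. But 0.01 is given only as an example, and section 10.4 leaves the detail to the SAP. Handling lung function in a corresponding manner does not require the same variance on a different scale. Stating each prior in the unit of its outcome is routine for anyone who fits the model.

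**Conclusion.** No change to the plan is called for. On its natural reading the sentence says that δ = 0 marks the same boundary as the t-test, which is true. Read as numerical equality it would be false under the prior described: 0.967 to 0.932 against 0.975 at z = 1.96, assuming a proportion scale, SD 0.15 to 0.35, full enrolment of 50 and 25, and the example variance of 0.01. The text does not assert that equality. Nothing in the plan depends on the gap, because no posterior threshold is set and no decision is tied to the probability of benefit. When the data favour the system, the gap errs on the cautious side. Rewording would alter no result. The open choice of variance and unit is ordinary missing detail for the SAP.
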